3.3.2.1 Guidelines for Management of Potential Adverse Events

Sections 3.3.2.2 – 3.3.2.19 present management guidelines or warnings/precautions for the following cabozantinib treatment-emergent adverse events/serious adverse events of interest:

- Gastrointestinal disorders (diarrhea, nausea and vomiting, dehydration [prostate cancer studies], stomatitis and mucositis)
- Hepatobiliary disorders (elevated ALT and AST)
- Hematological disorders

- Fatigue, anorexia, and weight loss
 - Skin disorders (palmar-plantar erythrodysesthesia syndrome [PPES] and rash)
 - Wound healing and surgery
 - Hypertension
 - Thromboembolic events (venous and arterial)
 - Proteinuria
 - QTc prolongation
 - Hypophosphatemia
 - Thyroid function disorders
 - Hemorrhagic events
 - Osteonecrosis of the jaw (ONJ)
 - Angioedema
 - Musculoskeletal and connective tissue disorders
 - Respiratory, thoracic, and mediastinal disorders
-

Please refer to the Investigator's Brochure for additional practice guidelines and management recommendations for these and other AEs potentially related to cabozantinib treatment (e.g. intra-abdominal and pelvic abscess; nervous system disorders; infections and infestations; and respiratory thoracic and mediastinal disorders) use in specific populations, and overdose and first aid measures for accidental cabozantinib exposure.

As with all investigational products, unknown AEs may occur. Subjects should be monitored closely for all AEs. As with other agents in development, additional AEs are unknown.

3.3.2.2 Gastrointestinal Disorders

The most common non-hepatobiliary GI AEs reported in clinical studies with cabozantinib regardless of causality are diarrhea, nausea, decreased appetite, vomiting, constipation, stomatitis and abdominal pain.

Diarrhea

Subjects should be instructed to notify their physician immediately at the first signs of poorly formed or loose stool or an increased frequency of bowel movements. Administration of antidiarrheal/antimotility agents is recommended at the first sign of diarrhea as initial management. Some subjects may require concomitant treatment with more than one antidiarrheal

agent. When therapy with antidiarrheal agents does not control the diarrhea to tolerable levels, study treatment should be temporarily interrupted or dose reduced per Table 3-4.

Table 3-4: Management of Diarrhea Associated with Cabozantinib

Status	Management
Tolerable Grade 1-2 (duration < 48 h)	
 • Continue with study treatment and consider dose reduction • Initiate treatment with an antidiarrheal agent (eg, loperamide 4 mg followed by 2 mg after each episode of diarrhea [maximum: 16 mg loperamide per day]) • Dietary modifications (eg, small lactose-free meals, bananas and rice) • Intake of isotonic fluids (1-1.5 L/day) • Re-assess after 24 hours: 
 ○ Diarrhea resolving to baseline bowel habits: gradually add solid foods and discontinue or decrease antidiarrheal treatment after 12 h diarrhea-free interval ○ Diarrhea not resolving: Continue/resume antidiarrheal treatment
Intolerable Grade 2, Grade 2 > 48 h, or ≥ Grade 3	
 • Interrupt study treatment • Ask subject to attend clinic • Rule out infection (eg, stool sample for culture) 
 ○ Administer antibiotics as needed (eg, if fever or Grade 3-4 neutropenia persists > 24 h) • Administer fluids (1-1.5 L/day orally or IV, as appropriate) for hydration or to correct electrolyte abnormalities • For Grade 3-4 or complicated lower grade diarrhea consider hospitalization and IV hydration • Re-assess after 24 h 
 ○ Diarrhea resolving to baseline bowel habits or Grade ≤ 1: consider restarting study treatment at reduced dose ○ Diarrhea not resolving: Start and or continue antidiarrheal treatment (eg, loperamide 4 mg followed by 2 mg after each episode of diarrhea [maximum: 16 mg loperamide per day]). Consider starting second line antidiarrheal or referral to gastroenterologist

In addition, general supportive measures should be implemented including hydration, correction of fluid and electrolyte abnormalities, small frequent meals, and stopping lactose-containing products, high fat meals, and alcohol.

Recurrent or prolonged diarrhea can be associated with anal or perianal skin erosions which increase the risk for anal abscesses, fistulas, or proctitis. Good personal hygiene should be emphasized. Regular examinations of the perianal region should be performed whenever diarrhea

has occurred during treatment with cabozantinib. Infections of the perianal region should be treated per local guidelines.

Nausea and Vomiting

Antiemetic agents are recommended as clinically appropriate at the first sign of nausea and vomiting or as prophylaxis to prevent emesis, along with supportive care in accordance to clinical practice guidelines. The 5-HT₃ receptor antagonists are recommended over chronic use of NK-1 receptor antagonists and dexamethasone (NK-1 receptor antagonists can induce or inhibit CYP3A4, and glucocorticoids induce CYP3A4 and thus could lower cabozantinib exposure (see Sections 3.4.4). Caution is also recommended with the use of nabilone, which is a weak inhibitor of CYP3A4. When therapy with antiemetic agents does not control the nausea, or vomiting to tolerable levels, study treatment should be temporarily interrupted or dose reduced per Table 3-3.

Dehydration may be associated with vomiting and monitoring for and correction of fluid and electrolyte disturbances should be implemented.

Stomatitis and Mucositis

Preventive measures may include a comprehensive oral examination to identify and treat any potential risk for complications before study treatment is initiated. Appropriate correction of local factors should be instituted as indicated, such as modification of ill-fitting dentures and appropriate care of gingivitis.

During treatment with cabozantinib good oral hygiene and standard local treatments such as nontraumatic cleansing and oral rinses (eg, with a weak solution of salt and baking soda) should be maintained. The oral cavity should be rinsed after meals, and dentures should be cleaned and brushed often to remove plaque. Local treatment should be instituted at the earliest onset of symptoms. Obtain bacterial/viral culture if oral infection is suspected and treat infection as indicated by local guidelines. When stomatitis interferes with adequate nutrition and local therapy is not adequately effective, dose reduction or temporary withholding of cabozantinib should be considered per Table 3-2 and Table 3-3.

3.3.2.3 Hepatobiliary Disorders

Elevations of ALT, AST, and bilirubin have been observed during treatment with cabozantinib. It is recommended that subjects with elevation of ALT, AST, and/or bilirubin have more

frequent laboratory monitoring of these parameters. If possible, hepatotoxic concomitant medications should be discontinued in subjects who develop increased values of ALT, AST, or bilirubin.

Subjects on this study may enter with increased ALT/AST serum levels up to $3 \times$ ULN. Dose reductions of study treatment should be considered in any subject who develops drug-related Grade 2 elevated ALT, AST, or bilirubin lasting longer than 1 week. A subject who develops Grade ≥ 3 elevated ALT, AST, or bilirubin should have study treatment held and restarted at a reduced dose (see Table 3-2) after ALT, AST, and bilirubin levels resolve to at least Grade ≤ 1 or baseline. In subjects with recurrence of drug-related Grade ≥ 3 elevated ALT, AST, or bilirubin at the lowest dose level, study treatment should be discontinued. In subjects who develop ALT/AST elevations $> 3 \times$ ULN in combination with a bilirubin elevation $> 2 \times$ ULN without reasonable other explanation, drug-induced liver injury should be suspected and cabozantinib treatment interrupted. Reinstitution of study treatment after recovery of ALT, AST, and bilirubin to Grade 1 or baseline level is at the discretion of the investigator.

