Table 3-3: Dose Modifications of Cabozantinib for Treatment-Related AEs

CTCAE v.4.0 Grade	Recommended Guidelines for Management^a
Grade 1 AEs	Add supportive care as indicated. Continue cabozantinib treatment at the current dose level if AE is manageable and tolerable.
Grade 2 AEs which are tolerable and are easily managed	Continue cabozantinib treatment at the current dose level with supportive care.
Grade 2 AEs which are intolerable and cannot be adequately managed	At the discretion of the investigator, cabozantinib should be dose reduced or interrupted. Note: It is recommended that dose holds be as brief as possible.
Grade 3 AEs (except clinically non-relevant laboratory abnormalities)	Cabozantinib should be interrupted unless the toxicity can be easily managed with a dose reduction and optimal medical care. Note: It is recommended that dose holds be as brief as possible.
Grade 4 AEs (except clinically non-relevant laboratory abnormalities)	Subjects should have cabozantinib interrupted immediately. Discontinue cabozantinib unless the following criteria are met: 
• Subject is deriving clear clinical benefit as determined by the investigator and agreed by the Sponsor• Toxicity can be managed with a dose reduction following recovery to Grade 1 (or baseline) and optimal medical care

AE, adverse event.

Note: The dose delay and modification criteria for specific medical conditions are provided in Section 3.3.2. For re-treatment criteria of study treatment after a dose hold see Section 3.3.1.1.

^a Study treatment dose adjustment is only needed if the toxicity was deemed related to cabozantinib treatment or had an unclear relationship to cabozantinib treatment.

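### For related, clinically relevant Grade 4 ALT, AST or bilirubin elevations, Table 3-3 and Section 3.3.2.3 set opposite stop-or-restart defaults, and no text says which prevails

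*Combined protocol and SAP*

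**What the plan says.** **General rule.** In Table 3-3 (Section 3.3), the Grade 4 row excludes clinically non-relevant laboratory abnormalities, a term the protocol does not define. For the remaining Grade 4 events it says: "Subjects should have cabozantinib interrupted immediately. Discontinue cabozantinib unless the following criteria are met". The criteria are "Subject is deriving clear clinical benefit as determined by the investigator and agreed by the Sponsor" and "Toxicity can be managed with a dose reduction following recovery to Grade 1 (or baseline) and optimal medical care". Footnote a limits dose adjustment to toxicity that is related to cabozantinib or of unclear relationship.

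**Liver rule.** Section 3.3.2.3 says that a subject with Grade 3 or higher ALT, AST or bilirubin "should have study treatment held and restarted at a reduced dose" once values return to Grade 1 or lower, or to baseline. A later sentence in the same paragraph covers suspected drug-induced liver injury: ALT/AST above 3 × ULN with bilirubin above 2 × ULN and no other reasonable explanation. Treatment is interrupted, and then: "Reinstitution of study treatment after recovery of ALT, AST, and bilirubin to Grade 1 or baseline level is at the discretion of the investigator".

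**Pointers.** The note under Table 3-3 says: "The dose delay and modification criteria for specific medical conditions are provided in Section 3.3.2". It also sends re-treatment after a hold to Section 3.3.1.1. That section lets a subject who has recovered from a possibly related toxicity restart at a reduced dose, without distinguishing grades.

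**Diarrhea.** The diarrhea table in Section 3.3.2.2 puts Grades 3 and 4 in one row. When diarrhea resolves it says "consider restarting study treatment at reduced dose".

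**The concern.** A Grade 4 transaminase or bilirubin value falls under both the general table and the liver section. The table starts from stopping and allows an exception that needs the Sponsor. The liver section starts from restarting and needs nobody's agreement. With up to about 8 sites (Section 2.5), two investigators following the protocol correctly could manage the same severe liver toxicity in opposite ways. One could re-expose a subject without the Sponsor review that the other regards as required.

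Within the liver section, a subject can satisfy the Grade 3 or higher rule and the drug-induced liver injury trigger together. The two sentences then give differently worded restart instructions.

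This is a patient-safety inconsistency in the wording. It does not affect sample size, power or type I error.

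**Working it through.** There is no design figure to reproduce. The check sets the texts side by side and then sizes the affected group.

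**1. Same subject, two rules: related, clinically relevant Grade 4 ALT, AST or bilirubin**

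| | Table 3-3, Grade 4 row | Section 3.3.2.3 |
|---|---|---|
| First action | Interrupt | Hold |
| Default after that | Discontinue | Restart |
| Benefit condition | Yes, clear benefit | None |
| Sponsor agreement | Yes | None |
| Recovery required | Grade 1 or baseline | Grade 1 or lower, or baseline |
| Dose if restarted | Reduced | Reduced |

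The texts agree on interruption, recovery and a reduced dose. They disagree on the default and on the two conditions. A subject who has recovered but has no clear benefit agreed by the Sponsor is discontinued under the first and restarted under the second. Both cannot be followed.

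**2. Do the other texts settle it?**

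- Section 3.3 and the Table 3-3 note both point to Section 3.3.2 for specific events. Neither says that Section 3.3.2 replaces the table's Grade 4 conditions.
- Section 3.3.1.1 permits restart at a reduced dose after possibly related toxicity. It does not split by grade and does not mention the Table 3-3 conditions. It also bars re-escalation after Grade 4 events in major organs, including hepatic events. That presupposes that some such subjects continue at a lower dose, which is possible under either rule.
- The laboratory exception could remove some Grade 4 values from Table 3-3. However, Section 5.4 counts laboratory abnormalities that change management, including a withheld or reduced dose, as clinically significant for this study, and Section 3.3.2.3 itself requires a hold at Grade 3 or higher. On the protocol's own wording the exception would rarely apply here.

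**3. Overlap inside Section 3.3.2.3**

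The drug-induced liver injury thresholds have no upper bound, so a subject with Grade 3 or higher ALT or AST and bilirubin above 2 × ULN meets both triggers. One sentence says restart at a reduced dose. The other leaves reinstitution to the investigator and names no dose. Section 3.3.1.1 may supply the dose, but Section 3.3.2.3 does not refer to it for this case.

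**4. Diarrhea table**

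The restart wording is permissive. A site can consider a restart and also apply the Table 3-3 Grade 4 conditions. The table omits those conditions but does not contradict them.

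**5. Scale**

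Inputs: related Grade 3 or higher rates from Table 1-3 (N = 2410), and 44 planned patients. The related column is used because of Table 3-3 footnote a.

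- ALT: 44 × 0.024 = 1.06, about 1.1 patients.
- AST: 44 × 0.019 = 0.84, about 0.8 patients.
- Either one: from 1.1 (complete overlap) to 1.06 + 0.84 = 1.9 (no overlap).

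The all-cause rates of 3.1% and 2.9% would give 44 × 0.031 = 1.4 and 44 × 0.029 = 1.3. Bilirubin is not listed in Table 1-3. The documents do not separate Grade 4 from Grade 3, so the Grade 4 count is a subset of unknown size and could be zero.

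**The case against.** The best reply is that the specific section governs. Section 3.3 sends specific events to Section 3.3.2, Section 3.3.2.5 describes Table 3-3 as general guidance, and the table's own column heading calls its content recommended. Section 2.6 cites Section 3.3.2, not Table 3-3, when listing reasons for mandatory discontinuation. This is a natural reading and may be what was intended. It remains an inference: no sentence says so, and the Sponsor-agreement condition is the kind of safeguard a site may hesitate to treat as displaced by silence.

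Three stronger readings are tempting, and the documents do not support them.

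- *That the diarrhea table also contradicts Table 3-3.* It does not, because its wording is permissive and both can be followed.
- *That suspected drug-induced liver injury may be restarted at any permitted dose.* Table 3-3 sends re-treatment to Section 3.3.1.1, which speaks of a reduced dose after possibly related toxicity. The two liver sentences can also be read together, with the investigator deciding whether to restart and the other text giving the dose. Nor is discretion plainly the laxer rule: deciding whether to restart can be more cautious than being told to restart. What stands is a missing dose statement or cross-reference for subjects who meet both triggers.
- *That the inconsistency undermines the primary analysis.* The endpoint counts radiographic progression or death (Section 8.1.1), and no analysis of discontinuations for toxicity is specified. An early stop could bear on the two-cycle evaluability rule and hence on replacement, but the documents give no basis for sizing this, and only one or two Grade 3 or higher ALT/AST cases are expected.

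**Conclusion.** The point holds in limited form. For related, clinically relevant Grade 4 ALT, AST or bilirubin elevations, the protocol gives two incompatible defaults and no rule of precedence. The overlap of the two liver triggers is a secondary ambiguity, and the diarrhea table has an omission that a cross-reference would close.

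The expected number of related Grade 3 or higher ALT or AST cases is about 1.1 to 1.9 of 44, with Grade 4 an unknown part of that. This assumes that the pooled single-agent rates, which come from other tumor types and several doses, carry over to this population. It also leaves out bilirubin, for which Table 1-3 gives no rate.

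The reason to act is the severity of the toxicity and the ease of the correction, not the numbers. Which rule is clinically right is not judged here.

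**What to change.** Reconcile Table 3-3, Section 3.3.1.1 and Section 3.3.2.3:

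- State which text governs Grade 4 ALT, AST and bilirubin elevations, and whether the clear-benefit and Sponsor-agreement conditions apply to them.
- Say what counts as a clinically non-relevant laboratory abnormality in Table 3-3, at least for liver values.
- In Section 3.3.2.3, give one restart rule for subjects who meet both the Grade 3 or higher criterion and the suspected drug-induced liver injury criterion, including where the dose level is found.
- In the diarrhea table, add a cross-reference saying whether the Table 3-3 Grade 4 conditions apply.

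The clinical team decides the content of each rule. The cost is a wording amendment; sample size, stage 1 and final thresholds, and the analysis plan are unaffected.

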3.3.2.4 Hematological Disorders

Hematological toxicities (ie, neutropenia and thrombocytopenia) and associated complications have been observed after administration of cabozantinib and may be managed with dose interruptions and/or dose reductions. Use of granulocyte colony-stimulating factor support for neutrophil recovery is allowed per investigator discretion and in accordance with accepted guidelines after the first incidence of clinically relevant cytopenia.

Complete blood counts with differentials and platelets should be performed regularly. Subjects with hematologic toxicities may require additional or more frequent laboratory tests according to institutional guidelines. Results of such tests are to be forwarded to the local laboratory data management vendor.

Febrile neutropenia or evidence of infection associated with neutropenia must be assessed immediately and treated appropriately and in a timely manner according to institutional guidelines.

Dose reductions or dose interruptions for anemia are not mandated but can be applied as clinically indicated. Supportive care such as red blood cell transfusions may be managed according to institutional guidelines.

3.3.2.5 Fatigue, Anorexia, and Weight Loss

Fatigue has been reported during treatment with cabozantinib. Common causes of fatigue such as anemia, deconditioning, emotional distress (depression and/or anxiety), poor nutrition, sleep disturbance, and hypothyroidism should be ruled out and/or these causes treated in accordance to standard of care. Individual non-pharmacological and/or pharmacologic interventions directed to the contributing and treatable factors should be given. Note: Chronic use of modafinil should be avoided because of its potential to reduce cabozantinib exposure (see Investigator's Brochure). Refer to Table 3-3 for general management guidelines.

Anorexia and weight loss should be managed in accordance to local standard of care including nutritional support. If fatigue, anorexia, or weight loss cannot be adequately managed, study treatment should be temporarily interrupted or dose reduced per Table 3-2 and Table 3-3.

3.3.2.6 Skin Disorders

Palmar-plantar erythrodysesthesia syndrome (PPES; also known as hand-foot syndrome), skin rash (including blisters, erythematous rash, macular rash, skin exfoliation, dermatitis acneiform, and papular rash), pruritus, dry skin, erythema, pigmentary changes, and alopecia have been reported in cabozantinib-treated subjects. All subjects on study should be advised on prophylactic skin care. This includes the use of hypoallergenic moisturizing creams, ointment for dry skin, and sunscreen with sun protection factor ≥ 30 , avoidance of exposure of hands and feet to hot water, removal of calluses, protection of pressure-sensitive areas of hands and feet, and use of thick cotton gloves and socks to prevent injury and to keep the palms and soles dry. Subjects with skin disorders should be carefully monitored for signs of infection (eg, abscess, cellulitis, or impetigo).

Early signs of hand-foot syndrome could be tingling, numbness, and slight redness or mild hyperkeratosis. Early manifestations include painful, symmetrical red and swollen areas on the palms and soles. The lateral sides of the fingers or peri-ungual zones may also be affected. Adequate interventions are required to prevent worsening of skin symptoms such as blisters, desquamations, ulcerations, or necrosis of affected areas. Aggressive management of symptoms is recommended, including early dermatology referral. Treatment guidelines for PPE related to study treatment are presented in Table 3-5.

In the case of study treatment-related skin changes (eg, rash, hand-foot syndrome), the investigator may request that additional assessments be conducted with the subject's consent.

These assessments may include digital photographs of the skin changes and/or a biopsy of the affected skin and may be repeated until the skin changes resolve.

Table 3-5: Management of Treatment-Emergent Hand-Foot Syndrome (PPES)

CTCAE v.4.0 Grade	Action To Be Taken
Grade 1	Study treatment may be continued at the current dose if PPES is clinically insignificant and tolerable. Otherwise, study treatment should be reduced to the next lower dose level ^a Start urea 20% cream twice daily AND clobetasol 0.05% cream once daily. Reassess at least weekly, if PPES worsens at any time or does not improve after 2 weeks, proceed to the intervention guidelines for Grade 2.
Grade 2	Study treatment may be continued if PPES is tolerated. Study treatment should be dose reduced or interrupted if PPES is intolerable. Continue urea 20% cream twice daily AND clobetasol 0.05% cream once daily and add analgesics (eg, NSAIDs/gamma-aminobutyric acid agonists) for pain control if needed. Reassess at least weekly, if PPES worsens or affects self-care, proceed to the intervention guidelines for Grade 3.
Grade 3	Interrupt study treatment until severity decreases to Grade 1 or 0. Continue treatment of skin reaction with clobetasol 0.05% cream twice daily AND analgesics. Resume study drug at a reduced dose if PPES recovers to Grade \leq 1. Discontinue subject from study treatment if PPES does not improve within 6 weeks.

CTCAE, Common Terminology Criteria for Adverse Events; NSAID, non-steroidal anti-inflammatory drug; PPES, palmar plantar erythrodysesthesia syndrome.

^a Permitted dose levels are defined by individual protocols.

